7.3 Protocol Deviations

All protocol deviations (important and non-important) will be listed by treatment group for the Randomized set with site 065-S .

All-important protocol deviations leading to exclusion from the PPS (see Section 5.10) will be listed for the ITTS-w-065-S and summarized by treatment group for the ITTS.

The protocol deviations will be identified before data are unblinded near database lock.

7.4 Demographics and Other Baseline Characteristics

Demographic and baseline characteristics will be listed for the ITTS-w-065-S and summarized by treatment group and overall for the ITTS. Standard descriptive statistics will be presented for:

- Sex;
- Race (American Indian or Alaska Native, Asian, African American, Native Hawaiian or Other Pacific Islander, White, Other);
- Ethnicity (Hispanic or Latino, Not Hispanic or Latino, not stated, unknown);
- Age (years) at screening (derived on eCRF);
- Age group (years) at screening (<65 years, ≥ 65 years) ;
- Height (cm) at screening visit;
- Weight (kg) at baseline;
- Body mass index (BMI) (kg/m²) (derived on eCRF) at baseline;
- BMI (<median, ≥ median) at baseline;

Statistical Analysis Plan

Sponsor Name: Poxel
Sponsor Protocol ID: PXL065-003

- Child-bearing potential (yes, no, not applicable);
- Randomization strata of T2DM status (T2DM patients, non-T2DM patients);
- Randomization strata of NASH CRN fibrosis scoring system (F1, F2/F3);
- Baseline LFC (%) (<median, ≥ median);
- Baseline LFC (%);
- Baseline ALT (U/L);
- Baseline HbA1c (%);
- Baseline FPG (mmol/L);
- Previously diagnosed with type 2 diabetes mellitus (Yes, No);
- Diabetes duration (Years);
- Patient currently treated for diabetes (Yes, No);
- Alcohol status (Never, former, current);
- If former or current, alcohol units consumed per week;
- Habitual cigarette smoking status (Never, former, current);
- If former or current, number of cigarettes per day;
- Other habitual tobacco or nicotine use (Never, former, current);
- Any history of drug abuse (Yes, No);
- Site pooling (Investigators speciality [Hepatologist, Others]);

The demographic and baseline characteristics table will be repeated in 4 additional populations in the ITTS: Diabetic patients, non-diabetic patients, F1 patients and F2/F3 patients. All of these populations will be based on the randomization strata. The derivation of the medians for BMI and LFC will be based on the subset populations.

For randomization strata, the stratification factors as used in the IWRS randomization will be summarized.

No formal tests of statistical significance will be performed on the demographic and baseline data.

Other baseline measurements, such as vital signs and ECG, will be summarized by treatment group with post-baseline measurements.

Demographic and baseline characteristics table will also be repeated in ITTS-w-065-S

7.4.1 Medical History

Medical history will be coded using the Medical Dictionary for Regulatory Activities (MedDRA) [Version 23.0].

All medical history will be listed for Safety set with site 065-S, and the number and percentage of patients with any medical history will be summarized for Safety set by system organ class (SOC) and preferred term (PT) for each treatment group sorting by descending overall frequency of SOC, and within SOC by descending incidence of PT.

7.4.2 Previous and Concomitant Medications

Medications received prior to or concomitantly with IMP treatment will be coded by using the World Health Organization (WHO) Drug Dictionary [Version WHODrug Mar 2020], Anatomical Therapeutic Chemical (ATC) Classification codes.

Prior medications and concomitant medications are defined as follows:

Prior medications are defined as medications taken within 28 days prior to informed consent form (ICF) signature and stopped before or on ICF signature date.

Concomitant medications are medications that are ongoing before and continue after the ICF signature

New medications are medications that are prescribed during the study (Starting after ICF signature).

If a medication cannot be classed as prior or concomitant after applying imputation rules for missing/incomplete dates, it will be classed as concomitant.

Prior, concomitant and new medications will be listed for the Safety set with site 065-S: and summarized separately for the Safety set, with summary tables displayed by treatment group.

The number and percentage of patients using each medication will be displayed together with the number and percentage of patients using at least one medication within each indication, WHO ATC-Level 1, WHO ATC-Level 3, therapeutic class, and PT. The number and percentage of patients using medication for each different indication will also be displayed.

7.5 Measurements of IMP Treatment Compliance

7.5.1 Compliance

Overall compliance based on IMP accountability will be presented for the double-blind treatment period by treatment group.

Compliance will be calculated using the following formula based on accountability records on the eCRF:

$$\frac{\text{Number of tablets taken}}{\text{Theoretical number of tablets to be taken during the period (based on visit days)}} \times 100$$

Theoretical number of tablets to be taken during the period (based on visit days)

Compliance as recorded in the eCRF will also be presented for each visit:

- Randomization Visit (V1) to V3, V3 to V4, V4 to V5, V5 to V6, V6 to V7 and V7 to V8

Percentage compliance will be listed for the Safety set with site 065-S: and summarized descriptively by treatment group for the ITTS and Safety set.

The following percentage compliance categories will also be presented:

Statistical Analysis Plan

Sponsor Name: Poxel
Sponsor Protocol ID: PXL065-003

- <80.0%
- ≥80.0% and ≤120.0%
- >120.0%

7.5.2 Overdose

This study will be blinded during the treatment period. Since the daily dose received will be unknown up to the end of the study, an overdose can only be identified relying on the number of tablets administered over a defined period of time.

An overdose is defined as any dose greater than the daily dose prescribed, equivalent to the intake of 3 or more tablets per day, in any of the treatment groups.

Overdose events will be listed for the Safety set with site 065-S .

Cases of overdose may constitute AEs or serious adverse events (SAEs) and will also be presented in the relevant AE/SAE summaries and listings, see Adverse Events (section 7.7.2) below.

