### 6.1 Description of Investigational Medicinal Product

PXL065 tablets contain 7.5 mg or 15 mg of PXL065 plus the excipients. The active pharmaceutical ingredient is the single, mono-deuterated (*R*)-enantiomer of pioglitazone, which is isolated as a

Placebo tablets will contain excipients alone. PXL065 tablet of each dosage strength has the same shape, size and appearance (including the same color, smell and taste) as its respective placebo tablet.

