**Table 2. Treatments to be administered in the 4 treatment groups**

Treatment Group	Number of Tablets (Total = 2 Tablets/Day)
PXL065 7.5 mg QD (7.5 mg/day)	1 tablet of PXL065 7.5 mg + 1 tablet of placebo ( matching PXL065 15 mg tablet )
PXL065 15 mg QD (15 mg/day)	1 tablet of placebo ( matching PXL065 7.5 mg tablet ) + 1 tablet of PXL065 15 mg
PXL065 22.5 mg QD (22.5 mg/day)	1 tablet of PXL065 7.5 mg + 1 tablet of PXL065 15 mg
Placebo	1 tablet of placebo ( matching PXL065 7.5 mg tablet ) + 1 tablet of placebo ( matching PXL065 15 mg tablet )

The double-blind treatment period will last for 36 weeks after Randomization Visit (V1).

The first dose from the new IMP kit dispensed during the visit should be taken on-site during the visit, as detailed in Section 7.2 Double-blind Treatment Period.

The last IMP intake will be at study site on the day of End-of-Treatment Visit (V8-EoT) (morning time; after completion of all pre-dose assessments).

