## 6.6 Packaging and Labeling

PXL065 and placebo tablets will be packaged in appropriate blister and will be labeled in English with respect to the regulatory requirements in the United States.

Two tablets, one of each size for the two dosages of PXL065 (15 mg and 7.5 mg, or their respective placebo), should be taken at each intake. The patient must strictly follow these indications.

**IMP kit:** An IMP kit contains 96 tablets (48 days), corresponding to 6 weeks of treatment with 6 additional daily doses to cover time-window between visits; and will be dispensed at each dispensing visit during the double-blind treatment period.

**IMP kit numbering:** The IMP kit number will identify medication packs.

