### 8.3.9 Overdose

Preclinical data showed that daily administration of PXL065 was well tolerated in the dog for 13 weeks at doses up to 15 mg/kg/day.

Clinical data available so far with PXL065 showed a good safety and tolerability profile in healthy subjects after single and repeated administrations of PXL065 up to 30 mg QD. The dose of 30 mg QD is the maximal dose tested in humans.

Overdose is defined as any dose greater than the daily dose prescribed, equivalent to the intake of 3 or more capsules per day, in any of the cohorts.

Any suspicion of overdose, whether or not associated with a AE must be reported to POXEL and Safety Provider immediately (within 24 hours of the Investigator's awareness) (contact details in Section 14. Annex 2. *Serious Adverse Event Contact Information*). Details of overdose and any AE associated with this will be reported by the Investigator in the eCRF system also.

These events will be managed, followed up and reported as any other SAE.

No specific antidote is currently available for PXL065 and only symptomatic therapy is possible.

Conclusion on overdose will be included in the final clinical study report.

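### The overdose definition treats a dose above the prescribed one as the same thing as three or more tablets, but with two tablet strengths they differ: in three of eight arm-by-size combinations, two tablets of one size already exceed the assigned dose

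*SAP*

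**What the plan says.** SAP 7.5.2 defines an overdose as "any dose greater than the daily dose prescribed, equivalent to the intake of 3 or more tablets per day" and applies this to every treatment group. Because the dose received is blinded until the end of the study, it adds that "an overdose can only be identified relying on the number of tablets administered over a defined period of time". Overdose events are then listed.

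Protocol 8.3.9 has the same definition with a different dosage form: "any dose greater than the daily dose prescribed, equivalent to the intake of 3 or more capsules per day". The same section requires even a suspected overdose to reach the sponsor and the safety provider within 24 hours of the investigator's awareness, and to be handled like an SAE.

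The regimen is set elsewhere in the protocol. Section 6.1 says "PXL065 tablets contain 7.5 mg or 15 mg of PXL065 plus the excipients". Section 6.6 requires at each intake "Two tablets, one of each size for the two dosages of PXL065", or the matching placebo. Table 2 gives the content by arm; the 22.5 mg group, for example, takes "1 tablet of PXL065 7.5 mg + 1 tablet of PXL065 15 mg".

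**The concern.** A dose threshold and a tablet count can be equivalent only if the tablets are interchangeable. Here they are not: a tablet holds 0, 7.5 or 15 mg, depending on its size and the arm. A patient who takes two tablets of one size, instead of one of each, stays at two tablets but may receive more drug than assigned. The first half of the definition calls that an overdose and the second half does not.

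The definition governs an expedited safety report and a safety listing. If sites or programmers apply the count, which is the method the SAP names, some intakes above the assigned dose may go unrecognised. Two sites could also classify the same event differently. Two of the three intakes concerned reach 30 mg, which Protocol 8.3.9 gives as the highest dose tested in humans.

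**Working it through.** **Inputs.** Content per tablet by arm, from Protocol Table 2: 7.5 mg arm, small tablet 7.5 mg and large tablet 0 mg; 15 mg arm, 0 and 15 mg; 22.5 mg arm, 7.5 and 15 mg; placebo, 0 and 0 mg. Small means the 7.5 mg size and large the 15 mg size, each including its matching placebo.

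**Formula.** Daily mg = (number of small tablets × content of small) + (number of large tablets × content of large). Excess = (daily mg − assigned mg) / assigned mg.

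**The plan's own figures.** One tablet of each size gives 7.5 + 0 = 7.5, 0 + 15 = 15, 7.5 + 15 = 22.5 and 0 + 0 = 0 mg/day, as Table 2 states. Two tablets on each of 48 days give 96 per kit, as Protocol 6.6 states.

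**Two tablets of one size in one day.**

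| Arm (assigned dose) | Two small | Two large |
|---|---|---|
| 7.5 mg | 15 mg (+100%) | 0 mg (−100%) |
| 15 mg | 0 mg (−100%) | 30 mg (+100%) |
| 22.5 mg | 15 mg (−33.3%) | 30 mg (+33.3%) |
| Placebo | 0 mg | 0 mg |

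Three of the eight cells exceed the assigned dose: 15/7.5 = 2.00, 30/15 = 2.00 and 30/22.5 = 1.333. Each is two tablets, below the count of three. The other five give less than the assigned dose, or 0 mg in the placebo arm.

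**The reverse direction.** Three tablets need not exceed the assigned dose. One small plus two large in the 7.5 mg arm is 7.5 + 2 × 0 = 7.5 mg. Two small plus one large in the 15 mg arm is 2 × 0 + 15 = 15 mg. Three small in the 22.5 mg arm is 3 × 7.5 = 22.5 mg. Placebo is always 0 mg. So neither half of the definition implies the other.

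**Would compliance show it?** The formula in Protocol 6.7.4 and SAP 7.5.1 divides total tablets taken by total tablets due. Over six weeks, 42 × 2 = 84 are due. Taking two of one size on some days leaves the total at 84, and 84/84 = 100%. The total does not reveal the swap; a count by size would.

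**The case against.** The strongest reply is that these intakes are not excluded. The first half of the definition covers them literally, and the 24-hour duty in Protocol 8.3.9 extends to suspicion. The sentence restricting identification to the tablet count is in the SAP only, and it does not say that size is to be ignored. This stands. A reader might infer that such intakes would be neither reported nor listed, but the documents support only that they may be missed.

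Other routes may also capture the error. Protocol 11.2 treats a patient dosing error as a significant deviation requiring contact with the sponsor, the diary records the dose taken (8.3.4), and the accountability logs include a dose field (6.7.4). None of these sections asks for a count by tablet size, and actual mg is blinded. However, the pharmacy manual, the overdose form and the eCRF guidelines are not available here, so it cannot be said that such counts are not collected.

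A reader might also infer that two tablets of one strength always exceed the assigned dose. Table 2 contradicts that: it is so in three of eight combinations. Nor is counting an extra placebo tablet as an overdose a defect in itself. Blinded staff cannot tell which tablet is placebo, so the count errs on the cautious side, equally in all arms.

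Finally, the error requires a departure from the one-of-each instruction and from the daily dose marked on the blister (Protocol 6.8), and Protocol 8.3.9 reports good tolerability in healthy subjects up to 30 mg QD. This limits the expected consequence but does not make the definition consistent.

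**Conclusion.** The definition contradicts itself and the trial's own regimen. In three of eight arm-by-size combinations, two tablets of one size exceed the assigned dose, by 100%, 100% and 33.3%, without reaching the count of three. Under the identification method in the SAP, these intakes may be missed in 24-hour reporting and in the overdose listing.

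The arithmetic rests only on Table 2 and on tablets being taken whole. The documents give no frequency for such errors; the blister marking and the dosing instruction suggest that it is low. What is affected is the completeness and consistency of safety reporting. A wider effect on the efficacy results should not be inferred: no endpoint, analysis set or test uses this definition. The point is worth correcting because the text is wrong as written and governs an expedited report, not because many cases are expected.

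**What to change.** The sponsor should reconcile the two halves of the definition in Protocol 8.3.9 and SAP 7.5.2 with each other, with Table 2 and with Protocol 6.6, and correct capsules to tablets in Protocol 8.3.9. Which half governs is the sponsor's decision; no dose or clinical rule is proposed here.

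In the SAP listing, show for each suspected overdose the number of tablets of each size, where recorded. The two sizes can be told apart without breaking the blind, since each active tablet looks like its own placebo (Protocol 6.1). The amount in mg can be assigned only after unblinding: two large tablets are 30 mg in the 15 and 22.5 mg arms and 0 mg in the 7.5 mg and placebo arms.

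The cost is wording in two documents and a count by tablet size. Timing limits the gain. SAP v3.0 is dated 12 August 2022 and the protocol planned the study to end in Q1 2022, so counts by size that were not recorded are unlikely to be recoverable. In that case the listing should say that it rests on total tablet counts.

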7.6 Efficacy

7.6.1 Primary Endpoint

7.6.1.1 Primary Analysis

The primary evaluation of efficacy will be based on MRI-PDFF. The primary endpoint will be the relative change in the percentage of LFC from baseline to Week 36 (V8-EoT) in the ITTS.

For patients who withdraw from the study at or after Week 12 (V4), the LFC will be assessed at ET as far as possible. With the assumption that the LFC assessed at or after Week 12 (V4) reflects what could have been observed at Week 36 (V8-EoT), the missing LFCs at Week 36 (V8-EoT) will be estimated by this value. For patients who withdraw before Week 12 (V4) or withdraw without any LFC assessment at or after Week 12 (V4), LFC missing values at Week 36 (V8-EoT) will be imputed using a multivariate imputation approach by fully conditional specification (FCS) regression method assuming missing at random (MAR) mechanism. The set of variables included in the multiple imputation model will be randomized treatment, type 2 diabetes mellitus status (T2DM patients versus non-T2DM patients), NASH CRN fibrosis scoring system (F1 versus F2/F3), and baseline LFC. The number of imputed datasets generated will be 1000 with the burn-out iterations set at 100. A minimum value of 0 and a maximum value of 50 will also be applied to restrict imputed LFC values, see

Statistical Analysis Plan

Sponsor Name: Poxel
Sponsor Protocol ID: PXL065-003

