### 9.5 Efficacy analysis

#### 9.5.1 Primary Endpoint: relative change in liver fat content (LFC)

The primary analysis of efficacy will be performed on the ITTS.

No adjustment for multiplicity will be considered.

Primary method to handle missing data: the LFC will be assessed at baseline and Week 36 (V8-EoT) only. For patients who withdraw from the study at or after Week 12 (V4), the LFC will be assessed at Early Termination Visit (ET) as far as possible. With the assumption that the LFC assessed at or after Week 12 (V4) reflects what could have been observed at Week 36 (V8-EoT), the missing LFCs at Week 36 (V8-EoT) will be estimated by this value. For patients who withdraw before Week 12 (V4) or withdraw at or after Week 12 (V4) but without any LFC assessment on treatment, LFC missing values at Week 36 (V8-EoT) will be imputed using a multivariate imputation approach by fully conditional specification (FCS) regression method assuming Missing At Random Mechanism. The set of variables included in the multiple imputation model will be further specified in the SAP.

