Appendix B: Sample SAS® code for analyses of efficacy endpoints for example SAS code.

Each of the complete datasets after imputation will then be analyzed in an analysis of covariance (ANCOVA) model adjusting for treatment and for randomization stratification factors, i.e. T2DM status (T2DM patients versus non-T2DM patients) and NASH CRN fibrosis scoring system (F1 versus F2/F3), and for the baseline LFC as a continuous covariate in the ITTS. Results from each complete dataset will be combined using Rubin's rule to provide the least square means (LSMs) for treatment groups at Week 36, standard error of the LSM, pairwise differences (PXL065 7.5 mg QD, 15 mg QD and 22.5 mg QD versus placebo) in LSMs, p-values and 95% CIs, see

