7.6.1.2 Sensitivity Analysis for the Primary Analysis

The imputation method described in the primary analysis will be repeated and each of the complete datasets after imputation will then be analyzed with non-parametric pairwise Wilcoxon tests stratified according to T2DM status and NASH CRN fibrosis scoring system. Hodges-Lehmann midpoint estimates along with their 95% confidence intervals will also be provided for the ITTS for each imputed data set and then combined using Rubin's rule, see Appendix C for example SAS code.

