7.6.2 Secondary Endpoints

7.6.2.1 Absolute Change in LFC

The absolute change in LFC (assessed by MRI-PDFF) from baseline to Week 36 (V8-EoT) will be analyzed in ANCOVA model adjusting for treatment, T2DM status (T2DM patients versus non-T2DM patients), and NASH CRN fibrosis scoring system (F1 versus F2/F3) and for baseline LFC as a continuous covariate. The method applied to missing data for the primary endpoint in Section 7.6.1.1 will also be utilized for this secondary endpoint. LSMS for treatment groups, standard error of the LSM, pairwise differences (PXL065 7.5 mg QD, 15 mg QD and 22.5 mg QD versus placebo) in LSMS, p-values and 95% CIs will

Statistical Analysis Plan

Sponsor Name: Poxel
Sponsor Protocol ID: PXL065-003

be presented. In addition, descriptive statistics for LFC and change from baseline will be calculated by visit within each treatment group.

The ANCOVA model validity will be checked using appropriate plots (studentized residuals vs predicted values, etc.).

The analysis described in Section 7.6.1.2 and 7.6.1.3, except for the ITTS-w-065-S will also be done for this secondary endpoint.

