Appendix B: Sample SAS[®] code for analyses of efficacy endpoints for example SAS code.

Statistical Analysis Plan

Sponsor Name: Poxel
Sponsor Protocol ID: PXL065-003

The binary response will also be analyzed using a logistic regression model adjusting for treatment, stratification factors, i.e. T2DM status (T2DM patients versus non-T2DM patients) and NASH CRN fibrosis scoring system (F1 versus F2/F3), and for the baseline LFC as a continuous covariate. Pairwise differences for each PXL065 treatment group vs placebo will be estimated in the model as ORs along with their p-values and 95% CI. The binary response will also be analyzed using the approach proposed by Ge et al. (2011), see Appendix C: Ge et al. code.

For each type of responder and analysis described above (CMH and logistic regression), two different methods of data handling will be applied:

- Multiple imputation as per Section 7.6.1.1
- No imputation and analysis set restriction (Restricting analysis to only include patients with Week 36 assessments)

Analysis of responder defined as relative reduction in LFC $\geq 30\%$ from baseline to Week 36 (V8-EoT), will be repeated in the ITTS-w-065-S , using multiple imputation as per Section 7.6.1.1.

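### Should missing Week 36 liver fat be imputed as relative change, the scale of the primary ANCOVA, instead of as raw LFC?

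*SAP*

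**What the plan says.** Protocol 9.5.1 imputes missing Week 36 LFC by FCS regression under missing at random and leaves one detail open: "The set of variables included in the multiple imputation model will be further specified in the SAP". SAP 7.6.1.1 keeps the method ("LFC missing values at Week 36 (V8-EoT) will be imputed using a multivariate imputation approach by fully conditional specification (FCS) regression method") and fills the open detail with randomized treatment, T2DM status, fibrosis stratum and baseline LFC, and asks for 1000 datasets. It adds that "A minimum value of 0 and a maximum value of 50 will also be applied to restrict imputed LFC values", limits that make sense only in LFC percentage points. A patient who withdraws at or after Week 12 and has an early-termination scan keeps that value, so only the rest are imputed.

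The same section defines the outcome: "The primary endpoint will be the relative change in the percentage of LFC from baseline to Week 36 (V8-EoT) in the ITTS". It continues: "Each of the complete datasets after imputation will then be analyzed in an analysis of covariance (ANCOVA) model adjusting for treatment", with the two strata and baseline LFC as the other covariates.

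The imputations are used again in three places:
- the Wilcoxon analysis (SAP 7.6.1.2): "The imputation method described in the primary analysis will be repeated";
- absolute change (SAP 7.6.2.1): "The method applied to missing data for the primary endpoint in Section 7.6.1.1 will also be utilized for this secondary endpoint";
- the four responder definitions (SAP 7.6.2.2): "Multiple imputation as per Section 7.6.1.1".

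SAP 7.6.1.3 repeats the primary and Wilcoxon analyses without multiple imputation. The sample code in Appendix B is redacted, so a transformation inside it cannot be confirmed or excluded.

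**The concern.** Write Y for Week 36 LFC and B for baseline. The endpoint is R = Y/B - 1. A regression of Y with one residual SD, s, implies that R has SD s/B, larger for patients with little liver fat. The ANCOVA assumes that the SD of R is the same for everyone. Unless all baselines are equal, both cannot hold.

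If the ANCOVA's assumption is the true one, low-baseline patients receive imputed relative changes that vary too much. Rubin's rule carries that excess into the standard error of the primary comparison. Imputation would then reduce the precision of the main test instead of protecting it, and the same draws feed the rank test and the relative-reduction responders.

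**Working it through.** **Inputs from the documents.** Difference -30%, SD 30%, two-sided 0.05, power 90%, 30 randomized per arm, 20% dropout (SAP 2.3); baseline LFC at least 8% (Protocol 5.1).

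**Inputs assumed, because the documents give none.** Baseline LFC mean 18 with SD 3.0 to 7.6, range 8-45; placebo change -5%; missing completely at random; how the SD depends on baseline; the share imputed.

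**1. The plan's own figure.** 2 x (1.960 + 1.282)^2 x (30/30)^2 = 21.0, so 22 per arm by the normal approximation. With the noncentral t, power is 0.8997 at 22 and 0.9125 at 23, so the stated 23 is right. With 20% dropout, 23/0.8 = 28.75 and 24/0.8 = 30, consistent with about 30 per arm.

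**2. The mechanism.** If the relative SD is 30% for everyone, the raw SD at baseline 18 is 0.30 x 18 = 5.4 points. Applied to all patients, 5.4 points is 5.4/8 = 67.5% at baseline 8 and 5.4/45 = 12% at baseline 45. The variances are 0.456 and 0.014 against a true 0.09, so the excess at the low end outweighs the deficit at the high end.

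**3. The share imputed.** With 20% dropout spread evenly over 36 weeks, 0.20 x 12/36 = 6.7% leave before Week 12 and 13.3% later. If 0 to 50% of the later group lack an early-termination scan, 6.7% to 6.7 + 0.5 x 13.3 = 13.3% are imputed. The full 20% is a ceiling.

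**4. Size.** Simulated trials of 4 x 30 patients (3000 per setting), bounded imputation, ANCOVA and Rubin's rule. Entries are the excess of the plan's SE over the SE from relative-scale imputation, across baseline SD 3.0 to 7.6:

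| What is assumed | 5% imputed | 10% imputed | 20% imputed |
|---|---|---|---|
| Relative SD constant | +0.4 to +3.0% | +0.8 to +5.8% | +1.3 to +10.1% |
| Relative SD falls as 1/sqrt(B) | +0.2 to +1.2% | +0.4 to +2.6% | +0.7 to +4.7% |
| Effect and SD constant in LFC points | -0.1 to -0.2% | -0.1 to -0.5% | -0.4 to -0.9% |

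A separate simulation with other baseline shapes gave +0.3 to +2.9% at 5% and +0.6 to +5.3% at 10% for the first row. For the third row it gave SE 0.0832 against 0.0831 at 10%.

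**5. Consequence in the least favourable row.**
- Power falls by 0.1-0.6 points at 5% imputed and 0.3-1.3 at 10%.
- Type I error at 10% imputed is 0.039-0.046 under the plan and 0.048-0.051 with relative-scale imputation, so the plan errs towards caution.
- The two estimates of the difference are within 0.5 point of each other under every assumption in the table.
- By the normal approximation, multiplying the SD by 1.06 takes power from 97.2% to 95.5% at 30 per arm, and from 92.4% to 89.2% at 23 per arm.

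**6. How much is miscalibration.** At baseline SD 6.5 and the 20% ceiling, the plan's SE is 9.37 and the relative-scale SE 8.71: 9.37/8.71 = 1.076. The plan's estimate itself has sampling SD 8.84, and 9.37/8.84 = 1.060. Part of the gap is therefore genuine extra variability, not an overstated SE.

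**The case for a change.** The strongest case for a change is that, if the ANCOVA's own assumption holds, imputing is worse than not imputing. At 10% imputed and baseline SD 6.5 the SE is 8.51 under the plan, 8.21 with observed cases only and 8.18 with relative-scale imputation. The imputation step was already revised once to add bounds (SAP 8), and one more run limited to the relative-change endpoints looks cheap.

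The arithmetic stands, and so does the point that the two models are not fully compatible. The case for replacing the primary imputation does not:

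- Nothing in either document favours a constant relative SD. SAP 2.3 gives one overall figure of 30% and does not say whether it varies with baseline. If effect and SD are constant in LFC points, relative-scale imputation makes the primary SE slightly larger.
- The alternative gives the same patient two imputed values that disagree, one for relative and one for absolute change, and splits the four responder definitions across two models. If effect and SD are constant in LFC points it moves the top-dose 30% responder rate by up to 1.1 points.
- The upper limit of 50 would become patient-specific: 50/8 - 1 = +525% at baseline 8 and 50/45 - 1 = +11% at baseline 45. The wording of Protocol 9.5.1 would also have to be departed from.
- The repeat without multiple imputation already shows any inflation. In the example above its SE is 8.21, almost the relative-scale value.

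SAP 7.6.1.4 does not say whether the primary-endpoint subgroups use imputed data, whereas SAP 7.6.2.5 says so for responders. That is a missing detail that programmers can settle, and it has no bearing on the choice of scale.

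**Conclusion.** This is a fair trade-off. Imputing the quantity that was measured and deriving all LFC endpoints from one completed dataset is coherent. Its possible price is an SE larger by about 0.4-3% at 5% imputed and 1-6% at 10%, if the relative SD does not depend on baseline; less under an intermediate pattern; and nothing if effect and SD are constant in LFC points. These ranges rest on an assumed baseline distribution, an assumed imputed share and data missing completely at random. There is no material bias and no added false-positive risk, and the power lost is about 0 to 1.3 points at 5-10% imputed. Protocol 9.1 describes the study as a Phase 2 trial for internal decision, and no decision would plausibly turn on a loss of this size. The plan can stand, with the no-imputation repeat as the check.
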